8.8 Safety analyses

Safety data from the run-in period will be summarized and listed on run-in analysis set.

Descriptive statistics will be provided for the following safety data. No inferential analysis of this safety data is planned. Any Vital signs, ECG, and Laboratory abnormalities of potential clinical concern will be described.

For the continuous safety measures, both actual and change values will be summarized at baseline and scheduled visit. Similar MMRM model as efficacy analysis will be conducted for hypoglycemia rate. For antibody continuous variables, the MMRM model will include the fixed, categorical effect of treatment group assignment, visit, treatment group-by-visit interaction and the other fixed effect terms investigator and baseline value as covariates. Contrasts of LS mean at each scheduled visit will be used to evaluate all pairwise treatment comparisons, and 95% confidence intervals for treatment differences in LS means will be computed for each visit. For categorical data analyses, Fisher's exact test or Chi-squared test will be used.

The following analyses will also be performed.

- Incidence of ADA response, incidence of positive cross-reactive ADA, and incidence of positive NABs
- Analysis of potential impact of TEAR status on efficacy and safety parameters such as HbA1c, FPG, insulin dose hypoglycemic rate, and incidence of any injection site allergic reactions and hypersensitivity
- Change in hypoglycemia rate (30 day adjusted) from baseline and incidence of hypoglycemic events at scheduled visits
- Incidence of TEAEs and SAEs
- Incidence of local allergic reactions, systemic allergic reactions and other adverse events
- Incidence of device-related safety assessment

To explore the potential ADA impact on subject's glucose control, the following analyses will be performed:

- The incidence of subjects with each of the three following criteria will be summarized descriptively (for categorical measures) by treatment:
 - 1) Meet TEAR criteria
 - 2) Increases in HbA1c of over 0.2% from baseline
 - 3) Increase in total dose from baseline
- Scatter plots of maximum tear values with HbA1c FPG and total daily insulin dose by treatment.

All the above analyses will be performed on the safety set.

In addition, graphical visualization of relationship between adverse events and treatment duration will be provided.

8.8.1 Adverse events

The frequency of AEs, SAEs, and AEs leading to discontinuation through Week 24 will be summarized based on safety analysis set or run-in analysis set.

All Adverse Events (AEs) will be classified by Primary System Organ Class (SOC) and Preferred Term (PT) according to the Medical Dictionary for Regulatory Activities (MedDRA) Version latest version. All subjects in the safety analysis set will be included in the summaries.

AEs will be classified as treatment emergent adverse events (TEAEs) are defined as follows:

TEAE: All AEs that occur after the first dose of study treatment medication after randomization through follow-up visit or 14 days after last dose [for subjects that do not have a follow-up visit] will be considered treatment emergent AEs.

Treatment-Related AEs: AE will be defined as related if causality is either definitely, probably or possible. AE will be defined as unrelated if causality is unlikely or not related. AEs where the causality is missing will be assumed to have “Reasonable possibility of relatedness.”

Grade AEs:

Grade AEs (serious and non-serious) in accordance with the NCI/CTCAE scale (available at

https://evs.nci.nih.gov/ftp1/CTCAE/CTCAE_5.0/) as presented below:

- **Mild** (Grade 1) asymptomatic or mild symptoms; clinical or diagnostic observations only; intervention not indicated
- **Moderate** (Grade 2) minimal, local or noninvasive intervention indicated; limiting age-appropriate instrumental activities of daily living
- **Severe** (Grade 3) Severe or medically significant but not immediately life threatening; hospitalization or prolongation of hospitalization indicated; disabling; limiting self-care activities of daily living

- **Life-threatening** (Grade 4) Life-threatening consequences; urgent intervention indicated
- **Death** (Grade 5) Death related to the AE.

Details for imputing missing or partial start dates of adverse events are described in Section 7.2.2. Imputed Adverse Event dates will be used for determining treatment-emergence.

Summaries of AEs will include the following:

- Treatment-emergent AEs
- Treatment-emergent treatment-related AEs
- Treatment-emergent AEs leading to study drug discontinuation
- SAEs
- Treatment-related SAEs
- AEs leading to death
- TEAE with the local and systemic allergic reactions

All TEAEs will be summarized by SOC, PT and treatment group as well as overall using frequency counts and percentages. In addition, an overall summary for the categories above will be prepared by treatment group and overall.

The number and percentage of subjects with at least one treatment emergent AE will be presented by treatment group as well as overall and events further summarized by maximum severity and relationship to study medication.

Where a subject has the same adverse event, based on preferred terminology, reported multiple times in the treatment period, the subject will only be counted once at the preferred terminology level in adverse event frequency tables.

Where a subject has multiple adverse events within the same system organ class in the treatment period, the subject will only be counted once at the system organ class level in adverse event frequency tables.

When reporting adverse events by severity, in addition to providing a summary table based on the event selection criteria detailed above, summary table will also be provided based on the most severe event during the treatment period - independent of relationship to study treatment.

Graphical visualization of relationship between adverse events and treatment duration will be provided. There are 2 graphs which are Time to AE Occurrence and Most Frequent On-Therapy AE Sorted by Risk Difference.

For run-in period, AEs and SAEs will also be summarized for run-in analysis set.

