During the 4-week run-in period with NovoLog® and Lantus®, the dose of insulin will be titrated (if required) to ensure diabetes control and patients who are receiving basal insulin other than Lantus® will be switched to this basal-bolus combination (Lantus®-NovoLog®). The run-in period ensures comparable drug exposure for all subjects, and increases the likelihood of comparable immune responses at the start of the treatment period. The run-in period also serves as an approach to single transition, wherein all patients entering the run-in period will be receiving NovoLog® for 4 weeks and following randomization to the treatment period patients will receive either NovoLog® or MYL-1601D allowing for assessment of switch from reference, NovoLog®, to the test product, MYL-1601D. A 24-week treatment period is an adequate period to detect differences in HbA1c and safety parameters of the treatment arms ([EMEA 2006](#)).

Dosing with NovoLog® during run-in period, and MYL-1601D and NovoLog® during treatment period will be guided by self-monitored blood glucose (SMBG)-based glucose

level assessments and by the Sponsor titration dose review team as detailed in the insulin monitoring titration plan.

Rescue criteria based on HbA1c are defined based HbA1c measurement performed on V11/week 12, so that a potential worsening of metabolic control in subjects during the study can be identified and therapy modified at the discretion of the Investigator.

A follow-up visit, 4 weeks after the end of treatment, will ensure the safety of all subjects after they stop the study medication and return to receiving market approved medications at the discretion of their physician.

Complete information for the study medication can be found in [MYL-1601D Investigator's Brochure](#) (IB).

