6.4 Visit 16 Follow up (Week 28) (telephone call)

- Discuss and check compliance to standard of care specifics as per American Diabetes Association 2019 guidelines, self-management of diabetes and life-style modifications with the subject.
- Record AEs, SAEs, local and systemic allergic reactions and hypoglycemic episodes
- Record concomitant medications since previous visit

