7.5 Other Safety Analyses

The analysis set for safety summaries is defined as all subjects who received at least one dose of study medication in the randomized treatment period. Safety data from the run-in period will be summarized and listed on run-in analysis set.

Treatment emergent adverse events and concomitant medications will be summarized and listed. All AEs that occur after the first dose of study treatment medication after randomization through follow-up visit or 14 days after last dose [for subjects that do not have a follow-up visit] after the last dose will be considered treatment emergent AEs. The number and percentage of subjects with at least one treatment emergent AE will be presented by treatment group and events further summarized by maximum severity and relationship to study medication.

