9.3 Management of Adverse Events

AEs or SAEs will be collected from the time the subject signs the informed consent form until the follow-up visit or 14 days after last dose of study medication. Pre-existing diseases or conditions (reported at visit 1 in medical history) will not be considered as AEs unless there is an increase in the frequency or severity, or a change in the quality of the disease or condition. An SAE deemed to be related to the study drug by the Investigator, and following consultation with Sponsor will be reported even after the Follow-up visit if reported by subjects.

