9.3.2.8 Notification

For SAEs, the active reporting period to Mylan, begins from the time the subject provides informed consent, which is obtained prior to the subject's participation in the study, i.e., prior to undergoing any study-related procedure and/or receiving investigational product, through and including the follow up visit or 14 days after last dose of study medication. Should an Investigator be made aware of any SAE occurring any time after the active reporting period, the SAE must be promptly reported to Mylan only in case of reasonable causality (i.e. suspected ADR).

The SAE reporting form is to be completed for all serious adverse events, signed by the Investigator, and emailed or faxed with supporting documentation (e.g., CRFs, hospital records, laboratory reports). Subject identity details (such as but not limited to name or clinic/hospital number) must not be visible on SAE forms or any supporting documentation provided by the Investigator. These should be "blacked out", and replaced with the site and subject's study identification number on every page.

At that time of first notification, the Investigator/designee should provide the following information via the SAE report form:

- Protocol number
- Reporter (study site and Investigator)
- Subject identification number
- Subject's age
- Investigational medicinal product
- Date of first dose of study treatment
- Date of last dose of study treatment, if applicable
- SAE term
- The seriousness criteria that were met
- Investigator's opinion of the relationship to the study treatment
- Severity
- Start and stop (if applicable) of the event (date and time)

- A brief description of the event, outcome to date, and any actions taken
- Concomitant medication at onset of the event
- Relevant medical history information
- Relevant laboratory test findings

If the initial notification of an SAE is by telephone, within 24 hours of the initial telephone notification the Investigator must email (preferred) or fax the written SAE report form that describes the SAE to the Mylan Product Safety and Risk Management department.

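### SAP 8.8.1 states a Week 24 limit for AE and SAE frequencies, but its own TEAE window runs to follow-up; the separate SAE and death tables are left without a clear window

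*SAP*

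**What the plan says.** The opening sentence of SAP 8.8.1 reads "The frequency of AEs, SAEs, and AEs leading to discontinuation through Week 24 will be summarized", on the safety or run-in analysis set. A few lines later the section defines a TEAE: "All AEs that occur after the first dose of study treatment medication after randomization through follow-up visit or 14 days after last dose", where the 14-day alternative is for subjects without a follow-up visit. Protocol 7.5 has the same definition: "after randomization through follow-up visit or 14 days after last dose [for subjects that do not have a follow-up visit".

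The protocol collects data to match. Section 9.3 says "AEs or SAEs will be collected from the time the subject signs the informed consent form until the follow-up visit", again with a 14-day alternative. Section 9.3.2.8 sets the active SAE reporting period "through and including the follow up visit or 14 days after last dose of study medication". Section 6.4 has the site do this at the Week 28 call: "Record AEs, SAEs, local and systemic allergic reactions and hypoglycemic episodes". Section 2.2 gives the reason for the visit, namely that it "will ensure the safety of all subjects after they stop the study medication".

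SAP 8.8.1 then lists its summaries. Some are labelled treatment-emergent, including the one for local and systemic allergic reactions. Three are not: SAEs, treatment-related SAEs and AEs leading to death. A later paragraph tabulates every TEAE by system organ class, preferred term and arm, with no Week 24 limit. The rules for counting a subject once, and the most-severe-event table, are worded for the treatment period.

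**The concern.** One section gives two end points for AE reporting and does not say which governs which table. For tables labelled treatment-emergent, the definition answers the question. For the SAE, treatment-related SAE and death tables it does not do so expressly, and the only window stated for SAE frequencies is the Week 24 one. An SAE or death in Week 26 would be collected and would count as a TEAE, yet could be missing from the table that reports SAEs or deaths by arm.

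Incidence of TEAEs and SAEs is a named safety endpoint (Protocol 3.2.2.2; SAP 4.3), and Protocol 7.3 makes it part of the totality of evidence. In an open-label trial the counting window for serious events is best settled in the text before analysis.

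**Working it through.** The plan states no figure on this point to reproduce. The check compares the stated windows and then measures the gap.

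**Windows by table**

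- *TEAE tables, including allergic reactions:* governed by the TEAE definition in SAP 8.8.1, so they run to the follow-up visit, or 14 days after last dose.
- *Hypersensitivity and immune-mediated events:* SAP 8.8.4, no Week 24 limit.
- *SAEs, treatment-related SAEs, AEs leading to death:* no treatment-emergent label. The opening sentence names SAEs and says Week 24.
- *Once-per-subject counting and maximum severity:* worded for the treatment period. SAP Table 1 and the visit-window table in SAP 8.1 place Visit 16 in a separate follow-up period, so this wording also stops short of the TEAE window.

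**Length of the gap**

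Inputs: end of treatment at Week 24 (Day 168) and follow-up at Week 28 (Day 196), from Protocol Table 1; the 14-day alternative, from SAP 8.8.1.

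- Completer with a Week 28 contact: 196 − 168 = 28 days; 28/196 = 14.3% of the post-randomization window.
- Completer without a follow-up visit: the window closes at 168 + 14 = 182 days; 14/182 = 7.7%.

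These are nominal days. SAP 8.1 assigns Days 162 to 182 to Visit 15. Reading Week 24 as the end of that range would shorten the gap to 196 − 182 = 14 days (14/196 = 7.1%) for the first group and to none for the second.

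**How many subjects**

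The documents give no SAE rate, so this is an illustration over a range. Assume a constant hazard, 500 subjects (Protocol 4.1) all followed to Week 28, and cumulative incidence q by Week 24.

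Incidence by Week 28: q28 = 1 − (1 − q)^(28/24). Subjects with a first event only in Weeks 24 to 28: 500 × (q28 − q).

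- q = 1%: q28 = 1.17%, about 0.8 subjects
- q = 2%: q28 = 2.33%, about 1.7 subjects
- q = 5%: q28 = 5.81%, about 4.0 subjects
- q = 10%: q28 = 11.57%, about 7.8 subjects

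These totals are for both arms together. The hazard may be lower after subjects leave study insulin.

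**The case against.** The best defence is that the section largely resolves itself. A Week 26 SAE is an AE after the first randomized dose and before follow-up, so it is a TEAE, and every TEAE is tabulated by arm. The opening sentence also covers the run-in set, for which a Week 24 limit has no function, so it may be only a general lead-in. The limit may attach only to AEs leading to discontinuation, since randomized treatment ends then. SAP 8.1 puts all subject data in listings, and SAP section 1 places the table templates in a separate document, which may already set the window.

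Most of this stands. A reader might infer that Week 24 to 28 events disappear from the report, or that allergic and immune-mediated events are at risk. The documents do not support either. The TEAE tables keep those events, the allergic-reaction summary is tied to the TEAE window, SAP 8.8.4 has no Week 24 limit, and the listings are complete. Nor do they support a single expected count of lost SAEs, because no rate is given.

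What the defence leaves open is the window for the SAE, treatment-related SAE and death tables. The grammar of the opening sentence does not confine the limit to discontinuations, and listings do not give frequencies by arm.

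**Conclusion.** The inconsistency is real and narrow. It affects three summaries and the treatment-period counting wording, not the TEAE tables, the allergic-reaction summary or the primary TEAR analysis. Under the opening sentence those three tables could omit events from the last 28 of 196 days (14.3%), or 14 of 182 days (7.7%) for a completer without a follow-up visit, on nominal visit days. An analyst who carries the TEAE definition through would lose nothing, so omission is possible rather than certain.

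The number of subjects affected is unknown. The range of about 0.8 to 7.8 in 500 rests on a constant hazard, full follow-up and an assumed incidence of 1% to 10% by Week 24. The point merits correction because the SAP already contains the window it needs.

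**What to change.** In SAP 8.8.1:

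1. Replace the Week 24 limit in the opening sentence with the TEAE window defined in the same section.
2. State that the tables of SAEs, treatment-related SAEs and AEs leading to death use that window, including the 14-day rule. A flat Week 28 limit would not do: it differs from the TEAE window for subjects without a follow-up visit.
3. Reword the once-per-subject counting rules and the maximum-severity table so that they refer to the same window instead of the treatment period.
4. If a table limited to Week 24 is wanted, label it as an additional on-treatment display. A separate follow-up column is optional.

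The cost is a few sentences in one SAP section and a check that the table templates agree. No new data are needed, and nothing changes in dosing or clinical management.

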9.2 Definitions

9.2.1 Adverse Events

An AE is defined as any untoward medical occurrence in a patient or clinical investigation patient administered a pharmaceutical product that does not necessarily have a causal relationship with the product. An AE can therefore be any unfavorable and unintended sign (including a new, clinically important abnormal laboratory finding), symptom, or disease, temporally associated with drug administration, whether or not related to the product.

The above definition covers also cases of

- Exacerbation of pre-existing diseases or conditions.
 - Pre-existing diseases or conditions will not be considered AEs unless there is an increase in the frequency or severity, or a change in the quality of the disease or condition.
 - Signs, symptoms, or the clinical sequelae of a suspected drug-drug or drug-food interaction.
 - Signs, symptoms, or the clinical sequelae of a suspected overdose of either study treatment or a concomitant medication. Overdose per se will not be reported as an AE/SAE unless this is an intentional overdose taken with possible suicidal/self-harming intent; this should be reported regardless of sequelae.

An AE will be defined as a TEAE if the first onset (or worsening, in the case of pre-existing disease) is after the first administration of MYL-1601D after randomization through follow-up visit or 14 days after last dose [for subjects that do not have a follow-up visit].

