9.3.2 Evaluation

9.3.2.1 Severity Assessment of Adverse Events

The clinical severity of an AE will be graded using the NCI-CTCAE Criteria Version 5 or the latest version. A copy of these criteria will be provided to each study site. If an AE is not listed in the CTCAE, its clinical severity will be classified as follows:

Table 6: Clinical Severity of Adverse Events

The Investigator will use the terms defined below to describe the maximum intensity of the AE.	
Grade 1 – MILD	Does not interfere with subject's usual function.
Grade 2 – MODERATE	Interferes to some extent with subject's usual function.
Grade 3 – SEVERE	Interferes significantly with subject's usual function.
Grade 4 - LIFE-THREATENING	Risk of death at time of event
Grade 5 – DEATH	Death related to AE

If an AE is graded 4 or 5 according to the above criteria (not applicable if using CTCAE criteria), then the AE meets the criteria for an SAE and the Investigator should immediately notify the Sponsor or designee as described in [Section 9.3.2.8](#).

It is important to distinguish between severe AEs and SAEs. Severity is a classification of intensity based on the CTCAE grading or on the above table, whereas an SAE is an AE that meets any of the regulatory specified criteria required for designation as seriousness described in [Section 9.2.4](#).

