7.2.3 Handling of missing or incomplete dates

Imputation rules for missing or partial AE start dates are defined below:

If only Day of AE start date is missing:

If the AE start year and month are the same as that for the first dose date, then:

- If the full (or partial) AE end date is NOT before the first dose date or AE end date is missing, then impute the AE start day as the day of first dose date;
- Otherwise, impute the AE start day as 1.

If Day and Month of AE start date are missing:

If AE start year = first dose year, then:

- If the full (or partial) AE end date is NOT before the first dose date or AE end date is missing, then impute the AE start Month and Day as the Month and Day of first dose date
- Otherwise, impute the AE start MONTH as January and the DAY as 1.

If Year of AE start date is missing:

If the year of AE start is missing or AE start date is completely missing, then query site and leave as missing.

For missing and partial adverse event end dates, imputation will be performed as follows:

If only the day of the month is missing, the last day of the month will be used to replace the missing day. If the day and month are missing or a date is completely missing, it will be considered as missing.

For the purpose of the derivation of adverse event duration, the following rules will be applied for missing/invalid onset/resolution time:

If onset time is collected and missing/invalid, onset time will be temporarily set to 00:00:01

If resolution time is collected and missing/invalid, resolution time will be temporarily set to 23:59:59

Imputation rules for missing or partial AE stop dates and the “continuing” variable indicated as “no” are defined below:

- Year is missing – date left missing.
- Month is missing – impute December.
- Day is missing – impute last date of that month.

If imputed AE stop date is before AE start date, AE stop date will be set to AE start date.

Imputation rules for missing or partial medication start dates are defined below:

If only Day of CM start date is missing:

If the CM start year and month are the same as that for the first dose date, then:

- If the full (or partial) CM end date is NOT before the first dose date or CM end date is missing, then impute the CM start day as the day of first dose date;
- Otherwise, impute the CM start day as 1.

If Day and Month of CM start date are missing:

If CM start year = first dose year, then:

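### The TEAE definitions conflict, leave out a non-serious run-in AE that worsens after randomization, and give no default for an AE without a start year

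*SAP*

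**What the plan says.** Three places define a treatment-emergent AE (TEAE).

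- SAP 8.8.1 counts these: "All AEs that occur after the first dose of study treatment medication after randomization through follow-up visit". Where there is no follow-up visit, the limit is 14 days from the last dose. Protocol 7.5 uses the same rule. It applies to either randomized product and has no worsening clause.
- Protocol 9.2.1 looks at when the AE began: "or worsening, in the case of pre-existing disease) is after the first administration of MYL-1601D after randomization". This adds worsening, limits it to pre-existing disease, and names only MYL-1601D.
- Protocol 9.3 shows what pre-existing means: "Pre-existing diseases or conditions (reported at visit 1 in medical history) will not be considered as AEs unless there is an increase". The increase meant is one of frequency or severity, and an altered quality also qualifies.

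On recording, Protocol 9.3 collects AEs from informed consent, so run-in AEs exist as records. Protocol 9.3.2.5 dates an AE from when it first occurred, except that an SAE is dated from when it became serious.

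On incomplete dates, SAP 8.8.1 decides treatment-emergence on the imputed date and refers to Section 7.2.2 for the rules. Section 7.2.2 concerns missing body weight; the AE date rules are in 7.2.3. There, a missing day is imputed only within the month of first dose, and a missing day and month only within the year of first dose. In both cases the first-dose date is used unless the AE ended before it. Otherwise: "If the year of AE start is missing or AE start date is completely missing, then query site and leave as missing".

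**The concern.** Protocol 2.2 presents the four-week NovoLog run-in as a way to assess the single transition from NovoLog to MYL-1601D. Protocol 3.1.1 lists injection site reactions in the totality of evidence for the primary objective. A local reaction that begins mildly in run-in and becomes worse after randomization is therefore relevant to what the design sets out to examine. Under the SAP rule such an event is classed by its run-in start date. It then drops out of the TEAE tables, including the allergic-reaction summary in SAP 8.8.1, which is restricted to TEAEs.

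The three definitions also disagree on whether worsening counts and on which product opens the window, so two programmers could class the same record differently. An AE with no start year cannot be classed at all, because the date that the rule needs stays missing.

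**Working it through.** The documents state no AE count or rate for this point, so there is no plan figure to reproduce. The check sets the definitions side by side and then runs test records through the rules as written.

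**Definitions compared**

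| Feature | SAP 8.8.1 and Protocol 7.5 | Protocol 9.2.1 |
|---|---|---|
| Window opens at | first randomized dose of study treatment, either arm | first dose of MYL-1601D |
| Worsening counts | not stated | yes, for pre-existing disease |
| Run-in AE that worsens | not covered | not covered, as pre-existing means reported at Visit 1 |

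Worsening of a Visit 1 condition is not lost: under Protocol 9.2.1 and 9.3 the increase is itself an AE, and if it arises after the first randomized dose it meets the SAP rule. The gap is confined to AEs that begin between Visit 1 and the first randomized dose. Within these it is confined to non-serious worsening, because an SAE is dated from the day it became serious.

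**Test records.** The first randomized dose is assumed to be 15 March 2019, for illustration only. The last column applies the definition proposed under the fix.

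| Record | Date after SAP 7.2.3 | TEAE under SAP 8.8.1 | TEAE under the fix |
|---|---|---|---|
| 1. Starts 10 Apr 2019 | 10 Apr 2019 | yes | yes |
| 2. Starts 1 Mar 2019, worsens to grade 3 on 1 Apr 2019 | 1 Mar 2019 | no | yes |
| 3. Start wholly missing, no end date | missing | cannot be decided | yes |
| 4. Start year missing, ends 1 Jun 2019 | missing | cannot be decided | yes |
| 5. Only 2019 known, no end date | 15 Mar 2019 | yes only if after means on or after | yes |
| 6. Mar 2019, day missing, no end date | 15 Mar 2019 | yes only if after means on or after | yes |
| 7. Apr 2019, day missing | no branch written | no rule, though plainly after first dose | yes |
| 8. Only 2020 known | no branch written | no rule, though plainly after first dose | yes |

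Record 2 is the substantive gap. Its result assumes that the site keeps one record with the first-occurrence date; no instruction to open a new record on worsening appears in either document. Record 4 is left unclassified although its end date shows that it was present after first dose. Records 5 and 6 show that the imputation works as intended only if the first-dose date itself counts.

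**Scale, on assumed rates only.** If 5% to 10% of the 500 subjects had an AE ongoing at randomization and 10% of those worsened:

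- lower end: 500 × 0.05 × 0.10 = 2.5 subjects
- upper end: 500 × 0.10 × 0.10 = 5 subjects

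Divided over two arms, this is 1.25 to 2.5 subjects per arm. Neither rate comes from the documents.

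**The case against.** The strongest reply is that these are gaps in wording with little effect on the planned tables. Much of it stands.

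- **One rule for both arms.** A reader might infer that worsening is lost only for MYL-1601D subjects. The documents do not support that: SAP 8.8.1 and Protocol 7.5 apply the same rule to a run-in AE that worsens on continued NovoLog. What differs is the meaning of the loss, since only the MYL-1601D arm changes product.
- **The MYL-1601D anchor.** A reader might infer that the NovoLog arm will show no TEAEs. That follows only from Protocol 9.2.1 read literally. The planned tables follow the SAP, which counts NovoLog events, so this is a conflict to reconcile and not a loss in the analysis.
- **One record per AE.** A reader might take "The Investigator will use the terms defined below to describe the maximum intensity of the AE" (Protocol 9.3.2.1) as saying that each AE is recorded once. It introduces the severity table for AEs not listed in the CTCAE and does not address the number of records. The exclusion of record 2 rests on the first-occurrence date and on the absence of a rule for worsening, not on this sentence.
- **Other reporting.** Run-in AEs have their own summary (SAP 8.8.1), and the SAE and AE-leading-to-death summaries are not labelled treatment-emergent. The event is reported somewhere, but not as treatment-emergent.
- **Undated AEs are likely to be rare.** Sites are queried first, AEs are asked about at each contact, and contacts are at most about four weeks apart. Records such as 7 and 8 can be classed by direct comparison, and the imputation that exists leans toward counting. What remains is an AE whose start year stays missing after the query.

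None of this supplies a rule for a non-serious run-in AE that worsens, or a default for an AE that cannot be dated.

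**Conclusion.** The concern holds as a conflict between definitions with one real gap. As written, a non-serious AE that begins in run-in and worsens after randomization is left out of the TEAE and allergic-reaction tables in both arms. In the MYL-1601D arm this can hide worsening after the switch that the run-in is meant to assess. The result assumes that worsening does not open a new record, on which the documents are silent.

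The number of events affected cannot be computed from the documents; the range in the working is only an illustration. No bias between arms is shown. The missing-year gap and the wrong cross-reference are minor but clear. The primary TEAR analysis does not use TEAE status and is unaffected. The definitions should be reconciled because the correction is specific and cheap.

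**What to change.** 1. Use one definition in Protocol 7.5, Protocol 9.2.1 and SAP 8.8.1: a TEAE is an AE with onset, or worsening in severity, on or after the first randomized dose of either MYL-1601D or NovoLog. Leave the end of the window as it is.
2. Record worsening of a run-in AE with its own date and grade, where this can still be captured.
3. State in SAP 7.2.3 that an AE whose start cannot be placed counts as a TEAE unless its end date is before the first randomized dose. Partial dates that already show the AE began after first dose are classed directly.
4. Correct the cross-reference in SAP 8.8.1 from 7.2.2 to 7.2.3.

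The cost is wording in the protocol and SAP and a CRF completion note, with no new visits or samples. TEAE counts may rise slightly. By SAP version 3.0 (2 March 2020), blinded ADA results from one site had already been reviewed (SAP 7.3), so data collection was under way. Worsening dates for AEs already recorded may not be recoverable, and the study report should say so if that is the case.
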